1. STUDY OBJECTIVES

The objectives of this study are:

Aim 1: Evaluate the effects of each behavior change technique message (i.e., BCT message) on daily adherence to weight loss behaviors in a 6-month micro-randomized trial among young adults (N=201). We will use an experimental microrandomized design, powered to detect both the effect of any BCT message (versus no message), and the unique effects of 7 different BCT messages (versus no message), on daily achievement of weight-related behavioral goals (weighing, active minutes, red food intake).

Aim 2: Determine whether the effects of BCT messages on proximal outcomes change over time. We will evaluate whether the effects of BCT messages (any message and by type of BCT) on daily achievement of weight-related behavioral goals change over time (day in program, time of day), and if so, the nature of the change (e.g., when effects disappear).

Aim 3: Assess whether the effects of BCT messages on proximal outcomes are moderated by participants' contextual factors. The primary moderators to be tested are participants' 7-day history of

contextual factors at the time of randomization (achievement of weight-related behavioral goals, streaks/lapses in self-monitoring, weight change, previous BCT messages received). Exploratory moderators include sex, age, and initial BMI status.

Efficacious intervention messages identified in this study will be used to create an optimized JITAI to be tested in a subsequent RCT examining weight losses at 6 and 12 months. This trial will expand our understanding of what BCT messages are effective, when they are effective, and for whom. Findings will guide how adaptive, behaviorally- and contextually-dependent messages are incorporated into future JITAIs for weight loss.

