2.2 Intervention Overview

All participants will receive a 6-month core intervention adapted from the Diabetes Prevention Program specially for young adults and to be delivered remotely via an automated program. The program, Nudge, will be delivered through a native smartphone app that includes weekly lessons, weekly tailored feedback, a native food log to track red foods, visual displays of behavioral progress, and in-app messages. All participants will receive a wireless scale and an activity tracker (Fitbit, San Francisco, CA) in the mail followed by an individual videochat session with an interventionist. For each of the 24 weeks of the program, at 3 scheduled time points per day, participants will be randomized to receive or not receive a BCT message promoting achievement of proximal weight management behaviors (weighing, activity, red food intake). Thus, participants will receive 0-3 messages per day. The primary outcome is same-day achievement of daily goals (weighing, active minutes goal, red food limit), evaluated among observations in which participants received a message compared to observations in which the participant did not receive a message.

Questions answered through Nudge MRT	

 Does providing a BCT message increase goal attainment on the same day it is delivered? (Aim 1) Do each of the BCT message types have different effects on goal attainment? (Aim 1) Do BCT messages' effects change over time? If so, what is the nature of the change (i.e., when does the effect disappear)? (Aim 2) Do BCT messages work differently when delivered under different contexts (e.g., time in program, time of day, previous dose of BCT messages, recent behaviors)? (Aim 3) 	
Intervention components to be tested across 3 behaviors: 7 behavior change techniques (BCT messages)	
1.4 Action planning	Message prompts detailed planning of performance of behavior via implementation intentions
1.6 Discrepancy between current behavior and goal	Message draws attention to discrepancies between a person's current behavior and previously set outcomes goals, behavioral goals, or action plans
2.7 Feedback on outcome of behavior	Message provides feedback on the outcome of performance of the behavior (i.e., weight)
3.1 Social support	Message advises on or provides social support for performance of the behavior
6.2 Social comparison	Message draws attention to others' performance to allow comparison with person's own performance

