We will test: 1) whether any intervention message (versus no message) increases adherence to daily weight loss behaviors among young adults, 2) whether a behavior-specific message (versus not receiving the behavior-specific message) increases adherence to the respective behavioral goal, and 3) finally the unique effect of each BCT message for the three proximal outcomes. We will use generalized estimating equations (GEE) with an independence working residual correlation matrix to account for nesting of observations within individuals.⁵⁸ and use Benjamini-Hochberg-Storey correction for multiple testing.⁵⁹

Analysis of whether effects of BCT messages change over time

We will also examine whether the effects of BCT messages on daily adherence to weight loss behaviors change over time (week in program, time of day) and, if so, the nature of the change (e.g., when effects disappear). Thus, we will expand upon the model described above by: 1) including linear and quadratic main effects of time and interaction terms, between an indicator of day in the program and treatment assignment, to test whether the treatment effect changes over time.⁵⁸ We will examine differences in the average and estimated time trends in treatment effects of receiving a behavior-specific message, and then the unique effect of each BCT message for the three proximal outcomes.

Analysis of whether effects of BCT messages are moderated by participants' contextual factors

We will evaluate whether the causal effect of receiving a BCT message interacts with participants' contextual factors, including past behaviors and individual characteristics. We will use standard moderation analysis within the GEE framework for these analyses, which involves the inclusion of main effects and interaction terms. Significant moderation effects will be probed using simple slopes analysis to determine the conditional region and direction of significance. The primary moderators to be tested are participants' 7-day history of contextual factors at the time of randomization (achievement of weight-related behavioral goals, streaks and lapses in self-monitoring, weight change, previous BCT messages received). Exploratory time-invariant potential moderators include demographic and health characteristics (e.g., sex, age, baseline BMI).

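### Aim 1 asks whether the seven BCT message types differ in effect, but the plan tests each type only against no message and specifies no between-type test or power for one

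*Combined protocol and SAP*

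**What the plan says.** The table of questions in section 2.2 (Intervention Overview) includes, under Aim 1: "Do each of the BCT message types have different effects on goal attainment". The same table asks separately whether sending a message raises goal attainment at all, so the question about differences is a distinct one.

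Section 1 (Study Objectives) says that Aim 1 is powered for the effect of any message and for "the unique effects of 7 different BCT messages (versus no message), on daily achievement of weight-related behavioral goals". It adds: "Efficacious intervention messages identified in this study will be used to create an optimized JITAI".

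Section 4 (Analysis of primary outcomes) lists three tests: any message against none, a behavior-specific message against not receiving it, and "finally the unique effect of each BCT message for the three proximal outcomes". For multiplicity it will "use Benjamini-Hochberg-Storey correction for multiple testing", without naming the family or the Storey tuning value.

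The nearest wording to a comparison is in the section 4 paragraph on change over time: "We will examine differences in the average and estimated time trends in treatment effects of receiving a behavior-specific message". The sentence goes on to the individual BCT effects. It names no contrast, null hypothesis or degrees of freedom.

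**The concern.** The question in section 2.2 has the null hypothesis that the seven effects are equal. The section 4 test has, for each type, the null hypothesis that its effect is zero. These are different hypotheses, and the second set of tests does not answer the first question. Seven equal, real effects estimated with ordinary sampling error can easily give some p-values below .05 and some above.

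At stake is one stated Aim 1 question. With only the planned tests, the material available for answering it would be the list of which types reached significance, and that list is not evidence that they differ.

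**Working it through.** **Inputs from section 4 (Sample Size and Power).** Alpha .05 (sidedness is not stated; two-sided assumed), 80% power, minimum detectable effect (MDE) .04 to .13 across the planned analyses, assumed effects .03 to .15, randomization probability 0.5, N = 201. Availability is named as an input but has no value.

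**The plan's own figures.** 168 × .83 + 84 × .17 = 153.72, rounded to 154; 201 × 154 = 30,954 person-days; 30,954 / 7 = 4,422 per type. These reproduce. The MDE range cannot be reproduced uniquely without availability, and the plan does not say which MDE applies to a single type. The simple formula 2.80 / √(n × .25) gives .084 at n = 4,422, so .13 and .084 are both used below as assumptions.

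**How often equal effects give a mixed result.** For one outcome, with seven equal effects, independent contrasts and power P each:

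Pr(mixed) = 1 − P⁷ − (1 − P)⁷

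- P = .50: 98%
- P = .80: 1 − .2097 − .00001 = 79%
- P = .90: 52%
- P = .95: 30%
- P = .99: 7%

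The rate exceeds 50% for P between 9.4% and 90.6%. If the per-type MDE is .13, that corresponds to d = .030 to .152, essentially the whole assumed range. If it is .084, it corresponds to d = .019 to .098, and at d = .13 the rate is only 6%.

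**Correlation from a shared no-message group (P = .80, uncorrected, simulated).** Correlation .125 (a no-message group seven times the size of each type's) gives 73%; correlation .5 gives 54%.

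**Multiplicity correction (P = .80, independent contrasts, simulated).**

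| Correction | Family | Mixed result |
|---|---|---|
| Plain Benjamini-Hochberg | 7 | 79% |
| Plain Benjamini-Hochberg | 21, all outcomes affected | 82% |
| Storey, λ = .5 | 7 | about 41% |
| Storey, λ = .5 | 21, all outcomes affected | about 15% |
| Storey, λ = .5, rejections capped at p ≤ .05 | 21, all outcomes affected | 79% |
| Storey, λ = .5 | 21, one outcome affected | about 90% |

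The low Storey rates arise because, when most effects are real, the estimated null proportion is small and p-values above .05 can be rejected. The value λ = .5 is an assumption.

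**A test that matches the question.** A 6-df Wald test of equal effects rejected in 4.8% to 5.2% of simulated trials with equal effects, at every power and correlation tried.

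**Its sensitivity, assuming a per-type MDE of .13.** SE = .13 / 2.80 = .0464.

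- Two types: detectable difference √2 × .13 = .18 with independent estimates (√2 × .084 = .12 if the MDE is .084).
- Joint test, two types at d = .15 and five at .03: the sum of squared deviations is .12² × (2 × 5 / 7) = .02057. The noncentrality is .02057 / .0464² = 9.55 with correlation 0, and 9.55 / (1 − .125) = 10.92 with correlation .125. Power at .05 is 62% and 69%. At .05/3, the strictest step of a correction over three outcomes, it is 45% and 53%.

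**The case against.** The strongest reply is that the formal Aim 1 text promises effects against no message, and that the messages carried forward are those found efficacious. For that selection the planned tests are the right ones, and an equality test would not change which types pass. This stands. A type that works but misses significance is lost through limited per-type power, and the change proposed here does not cure that.

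A reader might go further and infer that the plan will report equal effects as different, or will drop effective types because of this gap. The documents do not support that. Nowhere do they say that significance for one type and not another will be read as a difference. Nor do the figures show that a mixed result is the usual outcome in general: under the planned Storey correction the rate may be well below one half, and at high per-type power it is small with or without correction.

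It can also be said that the change-over-time paragraph mentions differences. Even read generously, it belongs to Aim 2 and defines no test of equal effects. The question in section 2.2 therefore remains without an analysis.

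**Conclusion.** The point holds as an omission: an Aim 1 question about differences between types has no between-type test and no stated power. The omission can be seen in the text and needs no simulation.

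The simulated rates illustrate why a split in significance cannot stand in for a test. The 79% figure rests on equal effects, independent contrasts, equal precision, two-sided .05 and 80% power each. Under the planned correction, the range of about 15% to 90% reflects details that the plan leaves open. The sensitivity figures depend on taking .13 as the per-type MDE.

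The validity of the tests against no message is not in question. This is a worthwhile, inexpensive improvement to the plan and leaves its primary tests intact.

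**What to change.** Keep the tests against no message. For each outcome, fit the seven BCT indicators in one GEE and add:

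1. a 6-df Wald test that the seven effects are equal, with the multiplicity correction applied across the three outcomes;
2. pairwise differences between types with confidence intervals.

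Both must account for which types could be sent at each decision point. Section 2.2 allows social reward only after effort or progress, while the discrepancy type addresses a gap between behavior and goals. Without this adjustment, unequal coefficients could reflect context and not technique. The SAP should therefore state how eligibility enters the joint test as well as the pairwise contrasts.

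State that any claim that types differ will rest on these contrasts and not on a split in significance. Name the family, tuning value and any cap for the Storey correction. Report the sensitivity: under the .13 assumption, a detectable difference of about .18 between two types, and joint-test power of 62-69% at .05 or 45-53% at .05/3 for the scenario above.

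The cost is SAP wording and contrasts from models that will be fitted anyway. The downside is that the trial may have to report that the types cannot be told apart. If the investigators do not want a between-type comparison, the alternative is to remove or reword the question in section 2.2.

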- *Sedentary Activity* at baseline, 3, and 6 months will be assessed with the Sedentary Behavior Questionnaire from the EARLY trials (Rosenberg et al., 2010; Lytle et al., 2014).

Psychosocial measures

- *Self-efficacy for eating*, measured using the Weight Efficacy Lifestyle Questionnaire (WEL-Q; 20 items).³⁵
- *Self-efficacy for exercise*, measured using the 12-item Self Efficacy and Exercise Habits Survey.³⁶
- *Self-regulation for exercise*, measured with the 10-item Exercise Goal-Setting Scale and the 10-item Exercise Planning and Scheduling Scale.³⁷
- *Motivation for making changes in diet* (15 items) *and exercise* (15 items), measured using the respective Treatment Self-regulation Questionnaires.³⁸
- *Perceived competence for diet* (4 items) *and exercise* (4 items).³⁹
- *Health-related quality of life*, measured using the CDC Healthy Days measure (CDC 1993).
- *Depressive symptoms*, measured using the Center for Epidemiological Studies Depression Scale (CES-D).⁴⁰

- *Weight control strategies*, measured with the Weight Control Strategies Scale (WCSS; 30 items).⁴¹
- *Hunger, restraint, disinhibition* measured using the Three Factor Eating Questionnaire (TFEQ; 51 items).⁴²
- *Perceived stress*, measured using the Perceived Stress Scale (PSS; 10 items).⁴³
- *Binge eating* measured using the revised Questionnaire on Eating and Weight Patterns (QEWP-5).⁴⁴
- *Social comparison orientation* measured using the Iowa-Netherlands Comparison Orientation Measure (INCOM; 11 items).⁴⁵
- *Weight-related information avoidance* (10 items).⁴⁶
- *Relatedness* measured with a scale adapted from Basic Need Satisfaction at Work Scale (3 items).^{47,48}
- *Message relevance* measured using 2 items from our previous work,⁴⁹ which was adapted from previous studies.^{50,51}

Other measures

We will assess several supporting measures, including sociodemographic characteristics, medical events, and medication use. Program engagement (app views, lessons accessed, feedback messages viewed, goals set or modified), process, and adherence measures (self-weighing, activity tracking, red food tracking, daily goal achievement) will be collected throughout the study period and used to calculate behavioral adherence in the prior 7 days and streaks and lapses in goal achievement. Program acceptability and satisfaction will be assessed using post-intervention program evaluation questions and in post-intervention semi-structured interviews after 6 months.

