4. STATISTICAL CONSIDERATIONS

Sample Size and Power

Our power analysis is based on a sample size calculator built in an R package (MRT-SS)⁵² for detecting proximal treatment effects in microrandomized trials developed by Liao et al,⁵³ expanding on more general results for sample size calculations for longitudinal trials from Tu et al.⁵⁴ Inputs to the sample size calculator are: desired alpha (.05), the number of outcome occasions ($T=168$ days for each proximal outcome), average probability of message availability each day, the randomization probability for a given message if it is available (0.5), and the standardized proximal treatment effect $\bar{d}_t = \sum_t d_t / T$ across all time points. Based on our prior research¹⁶ and the previous MRTs with published effects sizes,^{31,32,55} we assume that \bar{d}_t ranges from .03 to .15. Based on our previous studies with young adults^{56,57} and the pilot MRT,¹⁶ assuming 17% attrition by day 168, we estimated that a sample size of $N=201$ would be required to have an average of 150 usable days per person ($168 \text{ days} \times .83 + 84 \text{ days} \times .17 = 154$), for a total of 30,954 person-day observations ($N=201 \times 154$; i.e., over 4400 person-day observations per each of 7 BCT message interventions across 3 behaviors). This is consistent with a prior MRT that evaluated 6061 available decision points to test 2 different options for an intervention component (i.e., walking suggestions, anti-sedentary suggestions) among 37 participants.³² We will use all available data points in these analyses and test the sensitivity of our findings to dropout status by conducting completer-only and dropper-only analyses. The estimated minimum detectable standardized effect size with 80% power across the planned analyses ranges from .04 to .13.

Statistical Analysis Plan

Data analysis will be performed using R statistical software (version 4.0.3). Baseline demographic and descriptive characteristics will be summarized globally, using frequencies and percentages for categorical variables, and means and standard deviations (SD) for inherently quantitative variables. Prior to conducting data analyses, we will audit the data for completeness and quality, including missing data. We will evaluate response distributions to ensure that they meet assumptions of planned analyses (see below), including the detection of outliers.

Analysis of primary outcomes

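### The Aim 1 GEE specifies no pre-randomization covariates, although 7-day adherence history is already calculated; naming a fixed set would gain precision at almost no cost

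*Combined protocol and SAP*

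**What the plan says.** Section 4, Analysis of primary outcomes, lists three Aim 1 questions: any message, behavior-specific message, and each message type, for the three daily goals. One sentence gives the model: "We will use generalized estimating equations (GEE) with an independence working residual correlation matrix to account for nesting of observations within individuals". No covariate, link function or variance estimator is named.

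The next two subsections show what is added later. The time analysis expands the primary model by "including linear and quadratic main effects of time and interaction terms", so those terms are not in the primary model as written. The moderation analysis uses an approach "which involves the inclusion of main effects and interaction terms", and its main moderators are participants' "7-day history of contextual factors at the time of randomization".

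Section 3, Other measures, says that the engagement and adherence data will be "used to calculate behavioral adherence in the prior 7 days and streaks and lapses in goal achievement". The history variables therefore exist and are timed before each randomization.

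Under Sample Size and Power: "The estimated minimum detectable standardized effect size with 80% power across the planned analyses ranges from .04 to .13". The assumed average standardized effect "ranges from .03 to .15". The section does not say whether the SD used for standardizing is total or residual.

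**The concern.** Whether a person meets a daily goal is likely to depend on what kind of adherer that person is. The outcome definitions in section 3 point the same way: days without tracker wear, and days without complete food tracking, count as not meeting the goal, so disengagement becomes a run of failures. The plan itself treats streaks and lapses as informative, since it tests them as moderators.

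Under an independence working correlation with no covariates, that predictable part of the outcome is counted as noise. Validity is not at stake. What is at stake is precision for the effects of seven message types on three outcomes, tested with a multiplicity correction. With N fixed at 201, covariate adjustment is one of the few means of improving precision still open. Leaving the covariate set unwritten also leaves the choice between unadjusted and variously adjusted models to be made after the data are seen.

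**Working it through.** **1. The plan's own figures.** Usable days: 168 × .83 + 84 × .17 = 153.72, about 154. Person-days: 201 × 154 = 30,954; divided by 7 this is 4,422. These reproduce.

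The detectable range of .04 to .13 cannot be reproduced, because average availability is named as an input without a value. With two-sided alpha .05 (sidedness is my assumption), 80% power and randomization probability 0.5, a 1-df test gives MDE = (1.960 + 0.842)/√(n × 0.25):
- n = 30,954 (availability 1): .032
- n = 4,422: .084
- to reach .04, availability must be about .63; to reach .13, about .06.

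These values are consistent with the stated range but do not show which variance it assumes.

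**2. Where between-person variance goes.** With one randomization per person-day at probability p and independence weighting, the variance of the unadjusted effect is about (between-person + within-person variance)/(N × T × p(1−p)). If pre-randomization covariates explain a share R² of the outcome variance, the numerator is multiplied by 1−R² and the standard error by √(1−R²).

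**3. How much a 7-day history explains.** Assume equal correlation ρ (the ICC) between any two days of the same person, with outcome variance σ². The covariance of today's outcome with the mean of the prior 7 days is ρσ². The variance of that mean is σ²(1+6ρ)/7. Hence R² = 7ρ²/(1+6ρ). The documents give no ICC, so ρ is an assumed range. The last column applies the SE factor to the upper stated MDE and holds only if that MDE uses a total SD.

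| Assumed ICC | R² | SE factor | SE reduction | Equivalent N, 201/(1−R²) | .13 becomes |
|---|---|---|---|---|---|
| .1 | .044 | .978 | 2% | 210 | .127 |
| .2 | .127 | .934 | 7% | 230 | .121 |
| .3 | .225 | .880 | 12% | 259 | .114 |
| .5 | .4375 | .750 | 25% | 357 | .098 |

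Day-to-day persistence beyond the ICC adds a little, which is why yesterday's outcome is worth including. With ICC .3 and an added lag-one dependence of .2, R² was .267 in simulation, a 14% smaller SE.

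**4. Simulation check.** Setup: 201 people × 154 days, one 0.5 randomization per day, random person intercepts, identity link, cluster-robust SE, prior-7-day mean as the only covariate, 300 runs per setting. Bias was negligible with and without adjustment. The robust SE fell by 1% (ICC about .06, R² .015), 5% (.18, R² .10), 11% (.30, R² .21) and 17% (.40, R² .32), in line with √(1−R²).

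**5. Contrasts with behavior-dependent availability.** If a message type is available only after good, or only after poor, recent adherence, the history covariate varies less among eligible days. The documents do not give the rules, so two gates are assumed:
- Gate on the 7-day mean above or below half. ICC .3: R² .055 to .09, SE down 3% to 5%. ICC .5: R² .10 to .145, SE down 5% to 8%.
- Gate on yesterday's outcome. ICC .3: R² about .15, SE down 8%. ICC .5: R² about .25, SE down 13%.

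**The case against.** Five replies deserve weight.

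*The plan does not say the model is unadjusted.* Correct. A reader might infer that the model is stated to contain only the message indicator. The text supports less: none is specified. The sentence cites a methods paper that may imply control variables, and if those are intended the plan should list them.

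*The independence structure is a sound choice.* Also correct. A reader might infer that it is the defect. With cluster-robust SEs it gives valid inference, and it is a safe choice when treatment and history vary over time. Only the missing covariates are at issue.

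*The size is assumed.* This stands. Large between-person variation, or an equivalent of more than 350 participants, might be inferred from the ICC .5 row, but the documents contain no ICC, outcome rate or between-person variance. At ICC .1 or below the gain is trivial.

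*The gain is smallest where it is most wanted.* This stands in part. Social reward messages, for example, require prior effort or progress. For such contrasts the reductions in step 5 apply, not those in the table. Nor do the documents say which detectable effect belongs to which contrast, so the message-type analyses cannot be shown to be underpowered; .13 lies inside the assumed effect range.

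*Covariates can change the estimand.* Under a logit link they do, and no link is named for these binary outcomes. That is a reason to name the link along with the covariates.

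A reader might also infer bias from history-dependent message types. The stated 0.5 probability is conditional on a message being available, and a comparison within available occasions is unbiased without adjustment. Whether the analysis is restricted in that way is a separate question.

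**Conclusion.** The point holds as a precision and specification gap. No covariates are specified for Aim 1, pre-randomization adherence history is already calculated, and adjusting for it reduces the standard error without introducing bias.

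For contrasts using all person-days, the reduction is about 2% to 25% over assumed ICCs of .1 to .5, and about 7% to 12% at .2 to .3. It is less for message types whose availability follows recent behavior. These figures rest on an assumed ICC, a roughly constant correlation between days, and randomization that does not depend on history among the days analyzed. Carrying them over to the .04 to .13 range also requires that those effects use the total SD; if they use a residual SD, the stated range may already presuppose adjustment.

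Nothing here shows that the sample size of 201 is wrong or that the planned inference would be invalid.

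**What to change.** In section 4, Analysis of primary outcomes, prespecify for every Aim 1 model:
- covariates: proportion of the prior 7 days on which the same goal was met, whether it was met yesterday, day in program, and decision-point slot. Take the history only up to the end of the previous day, so that no message sent that day can affect it;
- the message indicator centered at its randomization probability for that decision;
- independence working correlation (kept), identity link and SEs clustered on participant, so that the estimate is a marginal risk difference;
- a short-history rule for the first week, such as using the days available so far, with a stated value for day 1.

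In Sample Size and Power, state whether .04 to .13 uses a total or a residual SD, and give the availability values used.

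The cost is SAP wording and the first-week rule. No new data are needed. If a logit link was intended, moving to an identity link changes the reported effect measure to a risk difference, so the choice should be fixed before outcome data are analyzed.

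### Aim 2 asks when message effects disappear, but the only program-day model is a linear-plus-quadratic trend, which can test for change but cannot reliably date the end of an effect

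*Combined protocol and SAP*

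**What the plan says.** Section 1 (Study Objectives, Aim 2) sets out to learn whether effects change over time and "the nature of the change (e.g., when effects disappear". The question table in Section 2.2 puts it more sharply: "what is the nature of the change (i.e., when does the effect disappear". The analysis plan in Section 4 repeats the question and then extends the primary model, a set of "generalized estimating equations (GEE) with an independence working residual correlation matrix", by "including linear and quadratic main effects of time and interaction terms, between an indicator of day in the program and treatment assignment". The stated purpose is "to test whether the treatment effect changes over time". The next sentence adds: "We will examine differences in the average and estimated time trends in treatment effects of receiving a behavior-specific message", and then the same for each BCT.

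Three things are not stated:

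- what counts as disappearance (a zero crossing, an interval that includes zero, or a threshold);
- whether the quadratic term, or only the linear one, is interacted with treatment;
- any flexible form of time (blocks or a spline), or any check of the quadratic shape.

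**The concern.** Testing whether an effect changes and dating its end are different tasks. A polynomial of low degree over the whole program is adequate for the first. For the second, its shape does much of the work. An effect that fades to zero and stays there is flat after it ends. A parabola cannot be flat over an interval, so it must cross zero, go negative and perhaps turn back up, or miss zero altogether. A straight line cannot be flat at zero after a decline either. This is an error of approximation, so more participants would not remove it.

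Section 1 says that the results will feed an optimized intervention for a later randomized trial and will show when messages work. A date read from the fitted curve could carry a shape artefact of several weeks into that design. A dip or late rise could be mistaken for harm or recovery.

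**Working it through.** **Inputs from Section 4, Sample Size and Power.** The length of follow-up is "the number of outcome occasions ($T=168$ days for each proximal outcome"; for the sample size, "we estimated that a sample size of $N=201$ would be required". Randomization probability is 0.5, attrition 17% by day 168, and the mean standardized effect .03 to .15.

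**Assumptions, not in the documents.** The true shape d(t); linear retention r(t) = 1 − 0.17·t/168; an additive effect scale with residual SD 1; availability a = 1 (also 0.07), because the plan names availability as an input but gives no value.

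**The plan's own figures.** 168 × .83 + 84 × .17 = 139.44 + 14.28 = 153.7, rounded to 154. 201 × 154 = 30,954, and 30,954 / 7 = 4,422. These reproduce. The minimum detectable effect of .04 to .13 cannot be checked without availability. The plan gives no figure for the timing of disappearance.

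**Method.** In large samples the fitted interaction is the weighted least-squares projection of d(t) on (1, t, t²), that is, the b that minimizes Σ r(t)·[d(t) − b0 − b1·t − b2·t²]².

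**Hand check: effect 1 to day 28, then 0, equal weights.** Let x = 2t/168 − 1, so the effect ends at x0 = −2/3. The Legendre coefficients are

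- c0 = (1 + x0)/2 = 1/6
- c1 = (3/4)(x0² − 1) = −5/12
- c2 = (5/4)(x0³ − x0) = 0.463

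The fit is −0.065 − 0.417x + 0.694x². Its roots are x = −0.128 and 0.728, or t ≈ 73 and 145. The minimum is −0.13 near day 109, and the end value is +0.21. The fitted effect thus reaches zero about 45 days late, is negative for about ten weeks, and ends at a fifth of its starting size. With a linear interaction only, 1/6 − (5/12)x is zero at x = 0.4 (t ≈ 118) and ends at −0.25.

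**Other shapes, retention-weighted, days 1 to 168.** End values are fractions of the starting effect.

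| True course | Quadratic reaches zero | Days late | Positive again | Day-168 value | Linear-only reaches zero |
|---|---|---|---|---|---|
| Linear to 0 at day 28 | 67 | 39 | 144 | +16% | 115 |
| Linear to 0 at day 56 | 80 | 24 | 147 | +15% | 120 |
| Linear to 0 at day 84 | 105 | 21 | 154 | +6% | 126 |
| Linear to 0 at day 112 | 138 | 26 | no | −4% | 135 |
| Linear to 0 at day 140 | 152 | 12 | no | −8% | 147 |
| Abrupt stop, day 56 | 110 | 54 | 162 | +3% | 126 |
| Abrupt stop, day 84 | 141 | 57 | no | −26% | 141 |
| Abrupt stop, day 112 | 150 | 38 | no | −37% | never |
| Half-life 14 days (below 10% by day 48) | 80 | – | 145 | +12% | 120 |
| Half-life 28 days | never | – | – | +9% (true 1.6%) | 135 |
| Half-life 56 days | never | – | – | +15% (true 13%) | never |
| Linear to 0 at day 168 | exact | 0 | no | 0 | exact |

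**Would the artefact show through noise?** Take Var(b) = [201·a·0.25·Σ r(t)·f·f′]⁻¹ with f = (1, t, t²) and a = 1. For linear declines ending on day 28, 56 and 84, the false day-168 effect has z = 1.6, 0.8 and 0.2 at mean effect .03; 3.3, 1.6 and 0.4 at .06; and 8.2, 4.0 and 1.1 at .15.

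**If disappearance means that the fitted 95% interval first includes zero (a = 1).** At mean effect .03, linear declines ending on day 84 and 112 are dated to day 62 and 69, which is too early. At .15 they are dated to day 92 and 117.

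**Alternatives, in expectation.** For linear declines ending on day 28, 56, 84 and 112, 28-day block effects first equal zero in the blocks starting on day 29, 57, 85 and 113, with no dip or return. A restricted cubic spline (interior knots at days 14, 28, 56 and 112, boundary knots at 1 and 168) reaches zero at about day 35, 68, 104 and 123, with a day-168 value within about 2% of the starting effect. It handles late abrupt stops less well: a stop at day 84 is dated to day 111, with an end value of +16%.

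**Precision.** SE per block = 1/√(201·a·0.25·Σ r). With mean retention 0.915, a 28-day block at a = 1 gives 1/√(201 × 0.25 × 28 × 0.915) = 0.028. At a = 0.07 it gives 0.105, rising to 0.11 in the last block. One week at a = 1 gives 0.056.

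**The case against.** The strongest reply is that the plan offers this model as a test of change, for which it is adequate, and never says that a zero crossing will be read off. That is correct, and the test stands. But the same paragraph poses the timing question and supplies nothing else to answer it.

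A reader might go further and infer that the model will always date disappearance weeks too late and builds in a false recovery near month 6. The documents do not support that, for four reasons.

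- They give no decay shape. A constant effect or a steady decline over 168 days is fitted exactly, and slow fades with little error.
- The late return belongs to early endings only. Linear declines ending on day 112 or 140, and abrupt stops at day 84 or 112, end falsely negative instead.
- Lateness is a property of the zero crossing. An interval rule with small effects can err the other way.
- With small effects the dip and return may not be statistically visible.

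Nor do the documents say that this model will fix how long each BCT keeps being sent. They say only that efficacious messages will form the optimized intervention.

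**Conclusion.** The concern holds in conditional form. The planned model can show that an effect changes but cannot reliably say when it ends, and disappearance is undefined.

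Among the assumed shapes that reach zero by day 112, a quadratic interaction crosses zero 21 to 57 days late, or about 3 to 8 weeks. A spurious dip and return can appear if the ending is gradual by about week 12 or abrupt by about week 8. Later abrupt endings give a falsely negative effect at week 24. If only the linear term is interacted, the date is also late, or for an abrupt stop at day 112 never reached, and the end value is usually falsely negative.

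All of this rests on assumed shapes, an additive scale and linear dropout. The gap in the plan does not depend on them. It affects a secondary aim, leaves the test of change intact and is cheap to repair, so it should be fixed but does not threaten the primary analysis.

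**What to change.** 1. Keep the polynomial interaction as the test of any change, and state whether the quadratic term is interacted with treatment.
2. For the timing question, add message effects by fixed program block (for example six 4-week blocks), or a restricted cubic spline with early knots, shown with confidence intervals. Blocks are the safer main display, since the spline can still misplace a late abrupt stop.
3. State that no disappearance day will be read from the polynomial alone.
4. Report timing as block estimates with intervals, mainly for the any-message and behavior-specific effects. Treat per-BCT timing as descriptive.

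Do not define disappearance as the first block after which every interval stays below a minimum effect. The precision is too low. For a truly null week at a = 1, the chance that the upper 95% limit lies below an illustrative margin of .10 is Φ(.10/.056 − 1.96) = 0.43. For a null 28-day per-BCT block at a = 0.07 and a margin of .13, it is Φ(.13/.105 − 1.96) = 0.235, and for five independent blocks in a row 0.235⁵ = 0.0007. Such a rule would date disappearance very late or never.

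The cost is a few lines in the analysis plan and one more model on the same data. The downside is that block or spline estimates are less precise than a quadratic: a standard error of about 0.03 per 28-day block at availability 1 and about 0.11 at an assumed 0.07, and timing resolved only to the block.
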